9.1 Efficacy assessments

Planned time points for all efficacy assessments are provided in the flowchart.

9.1.1 FGM

As indicated in the flow chart in Section $\underline{2}$, all subjects will have FGM profiles generated 3 times during the trial.

The FGM system used in this trial will be the FreeStyle Libre Pro system which consists of two parts:

- the sensor, applied on the back of the subjects' upper arm
- the reader, a hand held device kept at site and used to download data stored on the sensor

The sensor is pre-calibrated during manufacturing and requires no fingerstick calibration during use. The sensor measurements performed in the interstitial fluid are automatically calibrated to plasma equivalent glucose values, which will be shown on the display of the reader upon download of sensor data.

The FGM readings will be blinded to the subject as the reader will be kept at site. Upon download of FGM data at site, the investigator or delegated staff should review the FGM data for safety considerations taking into account all information detailed in the Operator's manual.

The FGM values generated should not be used for insulin dose titration.

9.1.1.1 FGM Reader setting

Each site will receive 2 readers; one to activate all subjects' sensors and download of their data and one as backup.

The FGM reader must be set up before use. The set up includes:

- date and time setting
- entry of the target glucose range. The range 70-180 mg/dL (3.9–10.0 mmol/L) should be used.

Time and date as well as level of battery should be verified each time the reader is used.

 Protocol
 Date:
 01 June 2018
 Novo Nordisk

 Trial ID: NN1250-4419
 Version:
 3.0
 3.0
 Status:
 Final Page:
 29 of 68
 29 of 68
 29 of 68
 20 of 68

9.1.1.2 Fitting and removal of the FGM sensor

Before the first fitting visit (Visit 2), subjects' eligibility must be confirmed.

The sensor must be applied on the back of the upper arm of the subjects, using the sensor applicator as described in the Operator's manual. When applied, a thin, flexible and sterile fibre is inserted just under the skin of the subjects, allowing the measurement of glucose concentration in the interstitial fluid.

The sensor must be activated by holding the site reader within 4cm (1.5inch) of the sensor. Successful start of the sensor must be checked as described in the Operator's manual.

The sensor will store the subject's glucose readings every 15 minutes for up to 14 days.

For further information on preparing, fitting, and removal of the FGM system, please refer to the Operator's manual.

If a subject withdraws consent during one of the FGM periods, a site visit must be scheduled in order to remove the sensor and download data to the reader.

9.1.1.3 **Duration of FGM periods**

The sensor has an in-use period of 14 days and will automatically stop recording data 14 days after insertion and activation.

As the data accuracy may vary during the first 24 hours after sensor fitting, the FGM data from the 1st day (24h) of each sensor period will be excluded from analysis.

Subjects must aim to use the sensor for 14 days in-use period.

In cases where the sensor is dislodged prematurely, the subject must be fitted with a new sensor as soon as possible. The cumulative number of day's data collected by the sensors must be a minimum of 14 days.

Additional fitting visit at site will not be considered an unscheduled visit.

For example: if the first sensor falls off 8 days after fitting, the subject then must be fitted with a second sensor to be worn for at least 6 days to obtain a total of 14 days of data.

At Visit 21 and Visit 39, it must be confirmed that a total of 14 days of data have been recorded, before subjects are switched to the other IMP or end treatment.

9.1.1.4 Wearing of the FGM sensor

Before each FGM periods, subjects must be instructed to follow the recommendations and limitations described in the Operator's manual and user guide while wearing the FGM sensor.

Protocol		Date:	01 June 2018	Novo Nordisk
Trial ID: NN1250-4419	CONFIDENTIAL	Version:	3.0	
		Status:	Final	
		Page:	30 of 68	

Subjects must be instructed to remove the FGM sensor prior to any X-ray, Computerised Tomography (CT) scan, high-frequency electrical heat (diathermy) treatment or magnetic resonance imaging (MRI).

The FGM periods should be conducted on days representing the subject's normal daily life. Before each FGM period, investigator or site staff should evaluate with subjects if planned activities would require the FGM assessments to be postponed (e.g. vacations, unusual strenuous exercise, overseas travel etc.).

FGM periods should not be planned across local daylight saving clock shifts to avoid major impact on time related endpoints, and subjects must be instructed to avoid overnight travel across time zones while wearing the FGM.

9.1.1.5 Transfer of FGM data

Data stored on the sensor must be downloaded at the site by holding the reader within 4cm (1.5inch) of the sensor. Data on the reader device must then be uploaded to the provided FGM Software program that allows upload of the FGM data from the reader, following the instructions from the user guide provided to sites.

The upload will be documented by the system directly.

The following information must be recorded and transferred into the eCRF for every FGM period:

- Serial number of the FGM sensor
- Sensor activation date and time
- Sensor removal date and time

The investigator or delegated staff must ensure that at least 14 days of data have been recorded according to Section 9.1.1.3. This can be done either on the reader or after upload of FGM data. The FGM data can be shared with the subject after each FGM period. In case several sensors are used within each FGM period, the data should only be shared once when all needed data have been downloaded from the reader, according to Section 9.1.1.3.

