6.3 Lifestyle restrictions

Change in lifestyle affecting glucose control must be avoided throughout the trial.

While wearing the FGM sensor, subjects will be asked to comply with requirements described in Section 9.1.1.4.

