8.1 Discontinuation from trial

The subject must be discontinued from trial, if the following applies:

- 1. Included in the trial in violation of the inclusion/exclusion/run-in exclusion criteria or randomised in violation of the randomisation criteria
- 2. Pregnancy
- 3. Intention of becoming pregnant
- **4.** Simultaneous participation in another clinical trial of an approved or non-approved investigational medicinal product.
- **5.** Initiation of bolus insulin treatment, GLP-1 receptor agonists or other diabetes medication(s) for more than 14 continuous days.
- **6.** Initiating use of real time CGM or FGM other than use specified by protocol

The primary reason for discontinuation of trial must be specified in the end-of-trial form in the CRF, and final drug accountability must be performed.

A treatment discontinuation session must be made in the IWRS.

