Appendix 8 Titration guideline

Titration guidelines have been developed, providing recommended dose adjustments at different PG levels to ensure that subjects receive an optimal treatment. However, it is recognised that insulin treatment should be individualised and the specific titration algorithms may not be applicable in certain clinical situations. Hence, it is important that other information, such as symptoms of hypo/hyperglycaemia, previous response to dose adjustments, other glucose measurements and other indicators of the subject's level of glycaemic control, is taken into consideration when decisions on dosing are made. The investigator is responsible for the treatment of the subjects and can therefore overrule the guidelines to avoid safety hazards.

Initiation of trial products

IGlar 100U/mL and IDeg should be injected subcutaneously into the thigh, upper arm (deltoid area) or the abdomen. The chosen region should be the same throughout the trial for each trial products. Rotation of injection sites within a given region is recommended.

Both IMPs should be taken once daily any time of the day, but at the same time every day. At randomisation (Visit 3) subjects will initiate treatment according to local label for the relevant IMP. At cross-over (Visit 21) the subjects should switch according to local label for the relevant IMP.

Dose adjustment of trial products during the trial

After randomisation the insulin dose will be evaluated and possibly adjusted once weekly by the investigator in connection with the scheduled visits/phone contacts during the titration periods. The dose adjustment will be based on the mean of three fasting SMPG values measured on two days prior to titration and on the day of the visit/contacts according to Table 8. If one of the SMPG values is below target (<3.9 mmol/L or 70 mg/dL) then dose adjustment will be based on the lowest SMPG values according to Table 9.

If one or more SMPGs values are missing, the adjustment should be performed on the remaining SMPG value(s).

Table 8 Increase of insulin dose

Mean pre-breakfast SMPG values		Increase of basal insulin	
		dose	
mmol/L	mg/dL	U	
3.9 - 5.0	70 – 90	No adjustment	
5.1 - 7.0	91 – 126	+ 2	
7.1 - 8.0	127 – 144	+ 4	
8.1 - 9.0	145 – 162	+ 6	
> 9.0	> 162	+ 8	

Protocol		Date:	01 June 2018	Novo Nordisk
Trial ID: NN1250-4419	CONFIDENTIAL	Version:	3.0	
		Status:	Final	
		Page:	68 of 68	

Table 9 Reduction of insulin dose

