2.3 Primary endpoint

The primary endpoint is the percentage of time spent in glycaemic target range (70-180 mg/dL (3.9-10.0 mmol/L), both inclusive) during the 2-week maintenance period. The FreeStyle Libre Pro device stores four measurements per hour and a subject with complete data will contribute with 14*24*4=1344 measurements from each 2-week period. The analysis will discard data from the first 24 hours as per communication with the vendor and so subjects with complete data will contribute with 13*24*4=1248 glucose recordings. The number of recorded measurements may be smaller for various reasons for subjects in the PP analysis set. Following ADA criteria we will demand that at least 70% of two weeks FGM measurements, corresponding to 10 days of FGM data, must be available for subjects to be included in the analysis. The percentage of time spent in glycaemic target range will be calculated as the number of recorded measurements in glycaemic

| Statistical Analysis Plan | | Date: | 23 January 2020 | Novo Nordisk |
|----------------------------|--------------|----------|-----------------|--------------|
| Trial ID: 1250-4419 | CONFIDENTIAL | Version: | 2.0 | |
| UTN: 1111-1203-0580 | CONFIDENTIAL | Status: | Final | |
| EudraCT no: 2017-004047-20 | | Page: | 8 of 17 | |

target range (70-180 mg/dL (3.9-10.0 mmol/L), both inclusive) divided by the total number of recorded measurements.

The primary estimand will be estimated by the primary endpoint analysed in a linear mixed model with treatment and period as fixed effects, subject as a random effect and with an unstructured residual variance matrix.

Using the unblinded data and before DBL, visual tools will be used to determine whether the data, including the primary endpoint, are normally distributed. If it is then found that the data are not normal, an appropriate transformation will be performed and this will be documented in a SAP or the DBL minutes.

Superiority of IDeg OD compared to IGlar 100U/mL OD with respect to percentage of time spent in glycaemic target range will be considered confirmed if non-inferiority is confirmed and the lower limit of the two-sided 95% confidence interval of the difference (IDeg OD - IGlar 100U/mL OD) is entirely above zero or equivalently if the p-value for the one-sided test of

H0: $D \le 0\%$ against HA: D > 0%

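### The period-1 FGM profile may be shown to the subject at the cross-over visit, which opens an avoidable route to treatment-dependent carry-over that the analysis does not address

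*Protocol*

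**What the plan says.** **Disclosure.** Protocol section 9.1.1 says that "all subjects will have FGM profiles generated 3 times": in the run-in and in each of the two maintenance periods. Section 9.1.1.5 then says: "The FGM data can be shared with the subject after each FGM period". Sharing is optional. If several sensors are used in one FGM period, data are shared once, after all the needed data have been downloaded.

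**Protections around FGM information.** Section 9.1.1 says: "The FGM readings will be blinded to the subject as the reader will be kept at site". It adds: "The FGM values generated should not be used for insulin dose titration". Section 6.3 says: "Change in lifestyle affecting glucose control must be avoided throughout the trial". Section 8.1 discontinues subjects for "Initiating use of real time CGM or FGM other than use specified by protocol".

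**Design.** The trial is open-label (section 7.5). Subjects go from one insulin to the other at Visit 21 without a washout, and 16 weeks of titration come before the second outcome window (section 5.1).

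**Analysis.** SAP section 2.3 analyses the primary endpoint in a mixed model "with treatment and period as fixed effects" and subject as random. The sensitivity analyses there concern the number of readings, a seven-consecutive-day rule and interfering substances. Neither document mentions feedback or carry-over. The items that section 9.1.1.5 requires in the eCRF for each FGM period are the sensor serial number and the activation and removal times. Whether data were shared is not among them.

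**The concern.** The period-1 profile is the subject's primary-outcome record on the first insulin, and the subject knows which insulin that was. What the profile shows can depend on the insulin, so what the subject does next (diet, routine, adherence to the titration scheme) can depend on it too. The 16-week titration gives the first insulin's own effect time to fade, but it does not remove what the subject has learned.

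In a two-period cross-over, a period-2 effect that depends on the period-1 treatment is differential carry-over. The treatment contrast absorbs half of it, and a model with treatment, period and subject terms cannot separate it from the drug effect. Because sharing is optional and unrecorded, the analyst would not know who received feedback, or whether the choice to share followed the result. At stake is the primary comparison, where the planned effect and the non-inferiority margin are both small.

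**Working it through.** **Inputs** (Protocol 10.1 and 10.3.1): planned difference 0.39 h per 24 h; SD of the within-pair difference 2.6 h; 401 per-protocol subjects; 85% power; one-sided 2.5%; margin 0.2 h per 24 h.

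**1. The plan's own figure.** A paired t-test sample size from the noncentral t distribution, with 0.39 h, SD 2.6 h, two-sided 5% and 85% power, gives 401. This matches the plan, as do the other five cells of the sample-size table. 401/0.85 = 471.8, so 472 randomised.

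**2. Percentage points of the day.**
- Effect: 0.39/24 = 1.63 points.
- Margin: 0.2/24 = 0.83 points.
- Standard error: 2.6/√401 = 0.130 h; 0.130/24 = 0.54 points.

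**3. Bias.** Let D be the true difference IDeg − IGlar, π the period-1-minus-period-2 effect, and λ_IDeg and λ_IGlar the period-2 effects of having seen a profile from that insulin. The expected period-1-minus-period-2 differences are:
- IDeg first: π + D − λ_IDeg
- IGlar first: π − D − λ_IGlar

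Half the difference between sequences is D − (λ_IDeg − λ_IGlar)/2, so

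bias = −(λ_IDeg − λ_IGlar)/2.

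Equal λ gives zero bias. Simulation agreed: equal carry-over of 0.3 h gave a mean estimate of 0.000 h, and differentials of +0.4 h and −0.4 h gave −0.20 h and +0.20 h at D = 0.

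**4. Illustration.** The documents give no λ, so the differentials below are assumptions. With the normal approximation, error at D = 0 is 1 − Φ(1.96 − bias/0.541), and power with a bias against IDeg is Φ((1.625 − bias)/0.541 − 1.96).

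| Assumed differential (points) | Bias (points) | One-sided error if bias favours IDeg | Power if bias is against IDeg |
|---|---|---|---|
| 0 | 0 | 2.5% | 85% |
| 0.5 | 0.25 | 6.7% | 72% |
| 1.0 | 0.50 | 15.0% | 55% |

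A bias of 0.25 is 15% of the planned effect (0.25/1.625), and 0.50 is 31% of it. A noncentral t calculation at an intermediate differential of 0.2 h (0.83 points) gives a consistent 11.7% error or 61% power.

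**5. Why a carry-over term is a poor substitute.** Assuming a within-subject correlation of 0.3 to 0.7, a test at this sample size has 20% down to 9% power to detect a differential of 0.40 h. That is the size that shifts the estimate by the whole margin (0.40/2 = 0.20 h).

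**The case against.** Much of the case on the other side stands.

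- **Run-in sharing.** A reader might infer that showing the run-in profile causes the same problem. It does not. The run-in precedes any trial insulin, so the feedback cannot depend on treatment; randomisation balances it, and it comes before both outcome windows.
- **Un-blinding.** A reader might infer that the outcome is un-blinded, or that sections 9.1.1 and 9.1.1.5 contradict each other. The documents do not support this. The trial is open-label, the reader stays at site, and no period-2 reading is visible to the subject while it is collected. A retrospective report is also use that the protocol specifies, so section 8.1 is not breached.
- **Existing limits.** FGM values are not for titration, lifestyle change is to be avoided, and both insulins are titrated to the same fasting target. These narrow the routes to carry-over, but none of them bars disclosure.
- **Small increment.** Subjects already record pre-breakfast glucose on three days around each weekly contact and know their insulin, so some treatment-specific feedback exists anyway. That reduces the added risk. It does not remove it, because the FGM profile covers the full day and is the outcome itself.
- **The assumed sizes.** A differential of 0.5 to 1.0 points is 31% to 62% of the planned drug effect, and would have to come from one report and persist for 16 weeks. At D = 0 the profiles do not differ on average in time in range, so a differential response would need another cause, such as hypoglycaemia pattern or expectation. Both remarks are fair, and the error rates are therefore illustrations only.

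**Conclusion.** The point holds in a narrow form. The protocol permits the period-1 profile to be shared from Visit 21, before or during the second treatment period, gives no reason for doing so, and plans no record or analysis that would reveal an effect. Bias requires two things that the documents do not establish: a response to feedback that differs by first insulin, and persistence through 16 weeks of titration. Its direction is unknown, so a reader should not infer that the result is tilted towards IDeg, or that bias has been shown at all.

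If the conditions were met, half of the differential would enter the estimate. With assumed differentials of 0.5 to 1.0 points that is about half to nine-tenths of a standard error (0.25/0.54 to 0.50/0.54). This is an avoidable weakness that is cheap to close, not an error in the sample size or the model.

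A related loose end: section 9.1.1 keeps FGM values out of titration, while Appendix 8 asks that dosing decisions consider "previous response to dose adjustments, other glucose measurements and other indicators of the subject's level of glycaemic control" and does not say whether FGM values are among them. The two passages must be reconciled.

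**What to change.** Amend Protocol section 9.1.1.5 along these lines: *FGM data from the first maintenance period may be shared with the subject only after the Visit 39 FGM period is complete, or after the subject has left the trial. The site's safety review at each download, and communication to the subject of any safety finding from it, are unchanged.* Run-in data need no restriction on this ground.

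Cost: one sentence in the protocol and the site instructions. Subjects see their period-1 profile about 18 weeks later. The sample size stays at 401 per protocol and 472 randomised.

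If deferral is not possible, record in the eCRF whether and when the profile was shared, and pre-specify a period-1-only sensitivity analysis. That analysis is free of carry-over but imprecise. Assuming equal variances and a within-subject correlation of 0.3 to 0.7, the single-period SD is 2.6/√(2(1 − ρ)) = 2.20 to 3.36 h. The standard error is then that SD × √(2/200.5) = 0.22 to 0.34 h, against 0.13 h for the cross-over estimate.

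Separately, state in section 9.1.1 and Appendix 8, in the same terms, whether FGM values count among the other glucose measurements considered in dosing decisions.

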9.1.2 Self-measured plasma glucose

Subjects must be instructed to perform pre-breakfast SMPG on the two days prior to, and on the day of the visit/contacts, from Visit 3 to Visit 39.

The BG meter provided by Novo Nordisk must be used for the measurements required in the protocol.

Subjects must also be instructed in how to transfer the results of the SMPG values into the diaries. The record of each SMPG value should include date and value. All data from the diary must be transcribed into the CRF during or following the site contact. If obtained via phone and a discrepancy is later detected, the values in the CRF must be corrected.

Protocol		Date:	01 June 2018	Novo Nordisk
Trial ID: NN1250-4419	CONFIDENTIAL	Version:	3.0	
		Status:	Final	
		Page:	31 of 68	

Occasional review by the investigator of the BG meter values stored in the memory of the BG meter and correct reporting of these in the diary is advised in order to ensure adequacy of the data reported in the trial database.

9.1.3 Clinical efficacy laboratory assessments

All protocol-required laboratory assessments, as defined in Appendix 2, must be conducted in accordance with the flowchart (see Section $\underline{2}$) and the laboratory manual.

9.2 Adverse events

The definitions of AEs and SAEs can be found in Appendix 4.

The investigator is responsible for detecting, documenting, recording and following up on events that meet the definition of an AE or SAE.

As the safety profile of the investigational medicinal products are well characterized, in this trial the selective safety data collection 7 will be limited to:

- SAEs
- AEs leading to permanent discontinuation of the IMP
- Medication errors related to trial products
- Pregnancies

The investigator must ensure that the above will be recorded in the CRF in a timely manner.

9.2.1 Time period and frequency for collecting AE and SAE information

All events meeting the definition of an SAE (see Appendix 4), AEs leading to permanent discontinuation of the IMP, pregnancies and medication errors related to trial products must be collected and reported.

These events will be collected from the first trial-related activity after obtaining informed consent and until the end of trial visit, at the time points specified in the flowchart. All SAEs will be recorded and reported to Novo Nordisk or designee within 24 hours of investigator's knowledge of the SAE, as indicated in Appendix 4. The investigator must submit any updated SAE data to Novo Nordisk within 24 hours of it being available.

[figure not shown]
After a subject has completed the trial, the investigators are not obligated to actively seek for safety collection in former trial subjects. However, if the investigator learns of any SAE, including a death, at any time after a subject has been discontinued from/completed the trial, and the investigator considers the event to be possibly/probably related to the investigational trial product or trial participation, the investigator must promptly notify Novo Nordisk.

The method of recording, evaluating and assessing causality of AE and SAE and the procedures for completing and transmitting SAE reports are provided in Appendix 4.

Protocol		Date:	01 June 2018	Novo Nordisk
Trial ID: NN1250-4419	CONFIDENTIAL	Version:	3.0	
		Status:	Final	
		Page.	32 of 68	

Medications errors related to trial products require additional data collection via a specific event form.

Timelines for reporting of AEs are listed in Figure 2.

Timelines are from the awareness of an AE Queries and follow-up requests to be resolved ≤ 14 calendar days

Figure 2 Decision tree for determining the event type and the respective forms to complete with associated timelines

